### 7.3 Variables

Key exposure, outcome and potential confounding variables are defined below in [Table 7-1](#). Additional details regarding definitions will be provided in the SAP to be developed separately, and will provide greater detail on the definitions of, the identification of and the controlling for confounders and/or effect modifiers.

Data will be collected through maternal interview(s) and questionnaires, medical records, a pregnancy exposure diary, a dysmorphology examination of live born infants, and the ASQ for live born infants. Maternal interview(s) include questions about pregnancy history, history of onset and other characteristics of MS, and current medication use. Other variables such as socio-demographics, gestational age, co-morbidities, concomitant medications, disease severity and duration, and other relevant potential confounders will be collected. Exposure and severity data will be collected at enrollment, at 20-22 weeks' gestation, 32-34 weeks' gestation, and 0-6 weeks after scheduled expected date of delivery or earlier if outcome has occurred prior to one of the previous interviews. For live births, infant data are collected at pregnancy outcome, and at approximately 12 months of age. Medical records will be requested from the participant's obstetrician as well as the healthcare provider treating her MS. Medical records are also obtained from the delivery hospital, and the child's pediatrician after birth and at 1 year of age.

Participants are asked to keep track of their pregnancy exposures and pregnancy related tests by filling out a pregnancy exposure diary throughout their pregnancy.

Live born infants are eligible for the dysmorphology examination which is performed by a study physician sometime in the infant's first year of life.

Mothers of live born infants are asked to complete the Ages and Stages developmental screening questionnaire at approximately one year of age.

**Table 7-1 Variables**

Variable	Role	Data source(s)	Operational Definition
Exposure to siponimod	Exposure	Maternal report Medical record	Maternal report of exposure to siponimod of at least one dose any time from 4 th days post first day of LMP prior to conception up to and including the end of pregnancy. Confirmation of exposure with medical records.
Dose of siponimod	Exposure	Maternal report Medical record	Dose of siponimod mg per day (maternal report and confirmation with medical records).

Variable	Role	Data source(s)	Operational Definition
Duration of siponimod use	Exposure	Maternal report Medical record	Weeks of siponimod use in pregnancy (maternal report and confirmation with medical records).
Indication	Exposure	Maternal report Medical record	Indication for use of siponimod (maternal report and confirmation with medical records).
Gestational age at time of initial exposure to siponimod	Exposure	Maternal report Medical record	Gestational age at the time of initial exposure to siponimod (maternal report and confirmation with medical records).
Major structural birth defect	Outcome – primary	Maternal report Medical record OTIS investigator review Dysmorphology Evaluation	The Registry adopts the term “major structural defect” (i.e., birth defect) for an abnormality usually referred to as a “congenital abnormality” and defines major structural defect as follows:  Any major structural or chromosomal defect defined and classified, using the CDC Metropolitan Atlanta Congenital Defects Program (MACDP) classification of birth defects ( CDC 2017 ).(including any intervention to correct the structural defect and its outcome) in any pregnancy including those ending in a live born infant or a pregnancy loss.
Minor structural defect	Outcome - secondary	Dysmorphology Evaluation	A defect which occurs infrequently in the population but which has neither cosmetic nor functional significance to the child and is identified using a study related checklist incorporated into the study dysmorphology examination of live born infants.
Spontaneous abortion	Outcome - secondary	Maternal report Medical record	Non-deliberate embryonic or fetal death that occurs prior to 20.0 weeks’ gestation.

Variable	Role	Data source(s)	Operational Definition
Stillbirth	Outcome - secondary	Maternal report Medical record	A non-deliberate fetal death that occurs at or after 20.0 weeks' gestation but prior to delivery.
Elective termination / abortion	Outcome – secondary	Maternal report Medical record	A deliberate discontinuation of pregnancy through medication or surgical procedures.
Premature delivery	Outcome - secondary	Maternal report Medical record	A spontaneous or induced delivery at <37.0 gestational weeks (as counted from LMP), reported by the mother and validated through the medical record.
Preeclampsia / Eclampsia	Outcome - secondary	Maternal report Medical record	Reported by maternal interview and confirmed with medical records.
Small for gestational age	Outcome - secondary	Maternal report Medical record	Birth size (weight, length or head circumference) $\leq 10^{\text{th}}$ percentile for sex and gestational age using National Center for Health Statistics (CDC, 2000) pediatric growth curves for full term infants. Prenatal growth curves specific to preterm infants will be used for premature infants (Olsen, 2010).
Postnatal growth deficiency	Outcome - secondary	Medical record	Postnatal size (weight, length or head circumference) $\leq 10^{\text{th}}$ percentile for sex and age using NCHS pediatric growth curves (CDC, 2000), and adjusted postnatal age for premature infants.
Screening for Developmental Milestones	Outcome - secondary	Neurodevelopmental questionnaires	Screening for neurodevelopment performed using the Ages and Stages Questionnaire (ASQ). An abnormal score is defined in the scoring guidelines.
Serious or Opportunistic Infections	Outcome - secondary	Maternal report Medical record	Defined as tuberculosis, x-ray proven pneumonia, neonatal sepsis, meningitis, bacteremia, invasive fungal infection, pneumocystitis, septic arthritis, osteomyelitis,

Variable	Role	Data source(s)	Operational Definition
			abcess (deep tissue), and infections requiring hospitalization, identified in live born infants up to one year of age.
Maternal Age (years)	Confounder	Maternal report	Maternal age (years) at due date, continuous and categorical (<25, 25-29, 30-34, >34).
Paternal Age (years)	Confounder	Maternal report	Paternal age (years) at due date, continuous and categorical (<25, 25-29, 30-34, >34).
Maternal Race	Confounder	Maternal report	Maternal (Caucasian/White, Black, Asian/Pacific Islander, Native American, Other).
Maternal Ethnicity	Confounder	Maternal report	Maternal (Hispanic, Non-Hispanic).
Maternal Education	Confounder	Maternal report	Maternal Educational Category (years of completed education <12, 12-15, >15).
Socioeconomic Category	Confounder	Maternal report	Hollingshead Socioeconomic Category based on maternal and paternal occupation and education (1-5).
Maternal Height	Confounder	Maternal report	Maternal height (cm).
Maternal Pre-pregnancy body weight	Confounder	Maternal report Medical record	Maternal pre-pregnancy body weight (kg) (confirm with medical record).
Maternal Pre-pregnancy BMI	Confounder	Maternal report	Maternal pre-pregnancy BMI (<18.5, 18.5-24.9, 25-29.9, >=30).
Number of times pregnant	Confounder	Maternal report Medical record	Number of times ever pregnant (1, 2-3, 4-5, >=6) (confirm with medical record).
Previous live birth or stillbirth deliveries	Confounder	Maternal report Medical record	Number of previous live birth or stillbirth deliveries (0, 1-2, 3-4, >=5) (confirm with medical record).

Variable	Role	Data source(s)	Operational Definition
Previous pregnancies ending in spontaneous abortion	Confounder	Maternal report Medical record	Number of previous pregnancies ending in spontaneous abortion (0, 1, 2, >=3) (confirm with medical record).
Previous pregnancies ending in elective termination	Confounder	Maternal report Medical record	Number of previous pregnancies ending in elective termination (0, 1, 2, >=3) (confirm with medical record).
Gestational age	Confounder	Maternal report Medical record	Weeks of pregnancy at time of enrollment, continuous and categorical (<13, 13-19.9, >=20): gestational age is calculated from the first date of LMP.
Referral source	Confounder	Maternal report	Source options: Sponsor, OTIS service, HCP, Internet, Other.
Geographic area of residence	Confounder	Maternal report	Geographic area of residence (e.g., US, Canada).
Disease Symptom/Severity measures	Confounder	Maternal report	Disease Symptom/Severity measures (exposed and disease-matched cohorts only).
Prenatal, Multivitamin, or Folic acid	Confounder	Maternal report	Prenatal, Multivitamin or Folic Acid supplement use by timing (began prior to conception, post-conception only, not taken at all).
Alcohol use in pregnancy	Confounder	Maternal report	Yes/No. Dose and frequency are captured.
Tobacco use in pregnancy	Confounder	Maternal report	Yes/No. Dose and frequency are captured.

Variable	Role	Data source(s)	Operational Definition
Prenatal diagnostic tests prior to enrollment	Confounder	Maternal report Medical record	Tests performed prior to enrollment (Ultrasound level 1, Ultrasound level 2, Chorionic Villus Sampling, Amniocentesis).
Prenatal diagnostic tests anytime during pregnancy	Confounder	Maternal report Medical record	Tests performed anytime in pregnancy (Ultrasound level 1, Ultrasound level 2, Chorionic Villus Sampling, Amniocentesis).
Maternal pregnancy exposure to a known human teratogen	Confounder	Maternal report Medical record	Maternal pregnancy exposure to a known human teratogen (e.g., Type I diabetes) (confirm with medical record).
Years since diagnosis of approved indicated disease	Confounder	Maternal report Medical record	Years since diagnosis of approved indicated disease.
Comorbid maternal medical history	Confounder	Maternal report Medical record	Comorbid maternal medical history (e.g. chronic hypertension, asthma)
Treatment history for the indicated disease	Confounder	Maternal report Medical record	Treatment history for the indicated disease
Pregnancy complications	Covariate	Maternal report Medical record	Pregnancy complications, including infection and gestational diabetes.

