- **Analysis subset:** for the primary outcome of major structural defects, the etiologically relevant window, with rare exceptions, is any exposure in the first trimester and the analysis subset in cohort 1 will be restricted to those with exposure to at least 1 dose of Mayzent from the 4th day post first day of to LMP prior to conception through the end of the first trimester. It is possible that some pregnant women in Cohort 1 could have exposure to Mayzent limited to the second or third trimester, and these would be considered separately. Duration and gestational timing of exposure to siponimod will also be considered.
- **Time period for identification:** major structural defects identified up to one year of age by the mother or the healthcare provider/medical record will be included in the primary analysis. Defects identified after that time frame will be described and considered separately.
- **Confirmation of defects:** independent confirmation of certain defects will be required. For example, a heart murmur thought to represent a ventricular septal defect

prior to 1 year of age will be included if it is confirmed as a heart defect by cardiac ultrasound. Similarly, a midline cutaneous marker at L2-L3 noted will be included as occult spinal dysraphism only if confirmed by appropriate imaging studies.

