#### 7.7.3.1.1 Analyses of the primary outcome

The primary outcome of interest, i.e. major structural defects, will be estimated in each cohort as a proportion (95% CI) using two denominators i) pregnancies ending in at least one live born infant and ii) pregnancies ending in at least one live born infant, stillborn, spontaneous abortion or elective termination. Data will also be presented by gestational timing of exposure.

For the primary endpoint, the exposure of interest is siponimod exposure at any time from the 4th day post the first day of the LMP prior to conception to the end of the first trimester, whether or not there is continued exposure to siponimod in the second or third trimesters. The primary comparison will be the rate of major structural defects between the siponimod-exposed group and comparison group 1 (disease-matched comparison group) among pregnancies resulting in at least one live born infant. A point estimate of the crude (i.e. unadjusted) risk ratio (RR) of the siponimod-exposed group versus comparison group 1, as well as its 95% confidence interval (CI) will be computed.

The same analysis will be repeated using the second numerator and denominator encompassing pregnancies ending in at least one live births, stillbirth, spontaneous abortion or elective termination, but excluding those lost-to-follow-up.

Due to the observational nature of the study, the above crude estimate of RR will be further adjusted for potential confounders (Rosenbaum, 2002), provided that there are sufficient numbers of events. A complete list of potential confounders, which includes but not limited to the baseline characteristics, will be provided in the SAP for each outcome prior to the final analysis, based on scientific knowledge including literature review.

As a primary approach, following Levenson and Yue, 2013, all potential confounders will be accounted for in the propensity score model.

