As a secondary approach, a sensitivity analysis will be considered and the following three criteria applied to identify confounders (Xu et al, 2018, Greenland et al, 1999): 1) by assessing each considered variable in a logistic regression model containing the exposure variable and the outcome variable to determine if inclusion of that single covariate changes the estimate of the odds ratio for exposure by 10% or more; 2) standardized mean differences (SMD) greater than 0.1; 3) association with the outcome with p-value < 0.2 in the unexposed cohort (comparison group 2). Care will be taken not to include those variables that are strongly associated with the exposure variable but only weakly associated with the outcome variable (e.g. instrument like variables) (Brookhart et al, 2006). The confounders identified above will be used to build the propensity score (PS) for exposure (Rosenbaum, 2002).

Balance in the covariate distributions before and after weighting will be assessed by providing the standardized mean differences of all covariates.

The primary analysis will be performed using the PS via inverse probability weighting (IPW).

As secondary analysis, the PS will be used in the so-called outcomes regression (Xu et al, 2018, Vansteelandt et al, 2014), i.e. a logistic regression model will be fitted with major structural defect (Y) as outcome, and exposure (A) and logit of propensity score (L) as regressors. In a second step, standardization will be performed to obtain the estimated causal risk ratio (Hernan and Robins, 2019). The CI for the causal risk ratio will be obtained by bootstrap.

Several sensitivity analyses will be performed for the primary outcome of major structural birth defects. One analysis will exclude those defects thought to be of chromosomal or genetic origin. Exposure to a known human teratogen is already included in the list of potential confounders for the siponimod-exposed group vs. comparison group 1. However, in the case where there are insufficient number of events to consider regression adjustment, a sensitivity analysis will be performed excluding participants with exposure to known teratogens in the siponimod-exposed group and comparison group 1 to address this potential confounder.

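### Prenatal testing at any time in pregnancy is labelled a confounder; unless the SAP drops it, the primary propensity score takes in a variable that largely follows exposure and can follow the defect

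*Protocol*

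**What the plan says.** Section 7.3 of the protocol introduces Table 7-1 with "Key exposure, outcome and potential confounding variables are defined below in" that table. Two rows on prenatal testing appear there, both with the role of confounder. One is limited to the time before enrolment: "Tests performed prior to enrollment (Ultrasound level 1, Ultrasound level 2, Chorionic Villus Sampling, Amniocentesis". The other has no time limit: "Tests performed anytime in pregnancy (Ultrasound level 1, Ultrasound level 2, Chorionic Villus Sampling, Amniocentesis". By contrast, the row for pregnancy complications, which also arise during pregnancy, is labelled a covariate.

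Section 7.7.3.1.1 sets the primary approach to confounding: "all potential confounders will be accounted for in the propensity score model". It then says: "The primary analysis will be performed using the PS via inverse probability weighting (IPW". The only caution about variable choice is "Care will be taken not to include those variables that are strongly associated with the exposure variable but only weakly associated with the outcome variable". That caution concerns instrument-like variables and stands in the description of the secondary selection approach.

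The same section defers the final list: "A complete list of potential confounders, which includes but not limited to the baseline characteristics, will be provided in the SAP for each outcome".

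On timing, Section 7.7.2.2 counts exposure for the primary outcome from day 4 after the LMP "through the end of the first trimester". Section 7.5.1 expects enrolment at 7-10 weeks after the LMP on average, and Section 7.4.3.2 has the interim interviews at about 20 and 32 weeks update prenatal test results. The two sensitivity analyses on testing in Section 7.7.3.1.1 use only tests and results from before enrolment.

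**The concern.** A confounder must be able to influence exposure, or share a cause with it, and must not be a result of the outcome. Testing up to delivery does not fit. Much of it takes place after the exposure that defines the cohort. A woman who learns that she was exposed to a drug with a fetal-harm warning (Section 5) has a reason to be tested more. A suspected defect is itself a reason for level 2 ultrasound, chorionic villus sampling or amniocentesis. If both links hold, testing is a common effect of exposure and defect, and balancing the cohorts on it distorts the association between them.

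The primary result of a drug-safety registry is at stake: a real increase in major structural defects could be partly weighted away. The planned checks would not show this. Standardised mean differences after weighting would look good precisely because testing had been balanced. The sensitivity analyses use a different testing variable. The crude risk ratio is reported as well, but a gap between crude and weighted results would be read as confounding removed.

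**Working it through.** **Benchmark.** The protocol has no figure on testing. Its relevant figure is the detectable risk ratio of 3.0 in the abstract and Table 7-4 (231 per group, 3% in the comparison group, two-sided alpha 0.05, 80% power). The arcsine approximation reproduces it:

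- h = 2·asin(√0.09) − 2·asin(√0.03) = 0.261
- 0.261 × √(231/2) − 1.96 = 0.85, so power is 80.2%.

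The pooled z-test gives 77.7%. The Fisher test that the table names gives 74.0%, and the text of Section 7.5.1 gives a detectable risk ratio of 4.4. Those are separate matters; 3.0 serves here only as the signal the study aims to detect.

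**Inputs.** From the protocol: cohorts 1:1 and comparison risk 3%. Assumed, because the protocol gives no values: the proportion tested among pregnancies without a defect, t0 (unexposed) and t1 (exposed), and the odds ratio OR for testing given a defect. No other confounding is assumed, so leaving testing out returns the true risk ratio.

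**Formula.** Let A be exposure, Y defect and T tested. In large samples, weighting on a score that contains T is standardisation over T:

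- P(T=1|A,Y=1) = OR·o/(1 + OR·o), with o = tA/(1 − tA)
- P(T=1|A) = P(Y=1|A)·P(T=1|A,Y=1) + P(Y=0|A)·tA
- weighted risk R_A = P(T=1)·P(Y=1|A,T=1) + P(T=0)·P(Y=1|A,T=0)
- weighted RR = R_1/R_0

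**One case in full** (true RR 3.0, testing 40% vs 70%, OR 5):

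- Tested given a defect: unexposed 3.333/4.333 = 0.769; exposed 11.667/12.667 = 0.921.
- Tested overall: unexposed 0.03×0.769 + 0.97×0.4 = 0.411; exposed 0.09×0.921 + 0.91×0.7 = 0.720; mean 0.565.
- Defect risk if tested: 0.0561 unexposed, 0.1151 exposed. If not tested: 0.0118 and 0.0254.
- R_0 = 0.565×0.0561 + 0.435×0.0118 = 0.0369. R_1 = 0.565×0.1151 + 0.435×0.0254 = 0.0761.
- Weighted RR = 0.0761/0.0369 = 2.07 instead of 3.0.

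**Range.**

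| Testing without a defect, unexposed vs exposed | OR for testing given a defect | True RR 1.0 becomes | True RR 2.0 becomes | True RR 3.0 becomes |
|---|---|---|---|---|
| 40% vs 60-80% | 3-10 | 0.58-0.82 | 1.15-1.64 | 1.71-2.45 |
| 40% vs 60-80% | 2 | 0.78-0.88 | 1.57-1.76 | 2.36-2.63 |
| 40% vs 40% | 3-10 | 1.00 | 1.95-1.98 | 2.85-2.95 |
| 95% vs 97% | 2-5 | 0.98-0.99 | 1.97-1.98 | 2.95-2.97 |
| any | 1 | 1.00 | 2.00 | 3.00 |
| 60% vs 40% | 3-10 | 1.21-1.37 | 2.40-2.66 | 3.56-3.89 |

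In the first row, putting the weighted risks into the pooled z formula lowers power at a true RR of 3.0 from 78% to 28-61%. That formula ignores the weights, so this is only indicative.

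**Detection instead of triggering.** Suppose testing does not depend on the defect but makes a defect 1.2-1.5 times as likely to be recorded. With 40% vs 70% tested and a true RR of 1.0, the crude RR is (0.7×1.2 + 0.3)/(0.4×1.2 + 0.6) = 1.06, or (0.7×1.5 + 0.3)/(0.4×1.5 + 0.6) = 1.13. Weighting on T would bring it back to 1.0.

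**The case against.** A reader might infer that the protocol commits this variable to the primary score. It does not go that far. Section 7.7.3.1.1 leaves the complete list to the SAP, outcome by outcome and on scientific grounds. Table 7-1 is one list for all outcomes, and the sentence on including all potential confounders follows directly after the one that defers to the SAP. Adjustment also depends on enough events, and only about 0.03 × 231 = 7 are expected in the comparison cohort. This objection stands, and the point is therefore conditional. It does not make the label right: the protocol assigns the role, allows the list to go beyond baseline characteristics, and has no guard against variables that follow exposure. A SAP that follows it faithfully would carry the row forward.

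A reader might also infer that the bias must run towards or below the null. The table shows otherwise. Level 1 ultrasound counts as a test, and Section 7.9 calls early prenatal testing highly prevalent. If the variable were coded as any test, both groups could be near 100% and the bias negligible; coding by type of test could leave a larger gap, and the coding is not stated. The comparison women also have MS and may take other MS drugs, so a large testing gap is not established. Defects confirmed only after birth need not have prompted any prenatal test. All of this limits the size claimed.

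The argument that adjustment corrects unequal detection has less force for this outcome. The primary analysis is confined to live births, counts defects to one year of age, and offers every live-born infant a blinded dysmorphology examination, so recording does not rest mainly on prenatal tests.

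Finally, tests before enrolment can also follow exposure, which may begin on day 4 after the LMP. That is true. However, women whose diagnostic test is already positive for a major structural defect are excluded, and the pre-enrolment row addresses selection on prior knowledge.

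**Conclusion.** The point holds in conditional form. Table 7-1 gives the wrong role to the any-time testing row, and the rule in Section 7.7.3.1.1 would carry that row into the primary score unless the SAP list for major structural defects leaves it out. Its inclusion can bias the primary risk ratio. Downward bias is the most plausible direction, but pushing a true 1.0 below 1 needs two things: exposed women tested more than the MS comparison women, and testing made more likely by a defect. Under the assumed 40% vs 60-80% and odds ratios of 3-10, a true 3.0 becomes about 1.7-2.5 and a true 1.0 about 0.6-0.8. With equal or near-universal testing the effect is close to nil, and with less testing of exposed women it reverses. All testing rates and odds ratios are assumptions. The protocol does not support a statement that the primary result is certain to be biased, or biased by a known amount.

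**What to change.** In Table 7-1, change the role of the any-time testing row from confounder to a descriptive or ascertainment variable. In Section 7.7.3.1.1, add a sentence that it does not enter the propensity score for major structural defects and that the pre-enrolment row is the only testing variable eligible for that score. Make the SAP list for this outcome agree.

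Leave the other listed confounders as they are. A general rule admitting only variables fixed before exposure or enrolment would be too wide: it would put in doubt alcohol and tobacco use in pregnancy and exposure to a known human teratogen, which Section 7.7.3.1.1 itself names as a potential confounder.

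The cost is one table cell and one sentence. Any-time testing is still collected and can be tabulated by cohort to describe ascertainment. No data collection or participant burden changes.
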